10.0 SECONDARY OUTCOMES ANALYSIS

The analysis of secondary outcomes will be considered exploratory; no adjustment for multiplicity will be performed. Secondary analyses will be based on the primary analysis population.

10.1 Low Luminance Visual Acuity (LLVA)

Change from baseline in LLVA total letters read in the study eye at the treatment completion visit and the post-treatment follow-up visit will be summarized and presented by participant for each cohort (Table 10, Listing 2).

10.2 Low Luminance Questionnaire (LLQ)

The LLQ is used to assess self-reported visual problems under low luminance and at night. The 32-item LLQ has six subscales: driving, extreme lighting, mobility, emotional distress, general dim lighting and peripheral vision. Each subscale score is derived by taking the average of a subset of questions from the LLQ, and a composite score is calculated as a weighted average of the subscales.¹⁹

Change from baseline in LLQ subscale and composite scores at the treatment completion visit and post-treatment follow-up visit will be summarized and presented by participant for each cohort (Table 11, Listing 3).

10.3 Dark Adaptation Times

A similar analysis to the primary outcome analysis for dark adaptation times described in Section 9.1 will be conducted comparing baseline to post-treatment follow-up visit in each cohort (Table 9, Listing 1).

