Design: This is a prospective, uncontrolled, single center, pilot study to investigate the potential efficacy and safety of vitamin A palmitate dosing in improving dark adaptation in participants with AMD and abnormal dark adaptation. Participants in the first cohort were instructed to take 16,000 IU of vitamin A palmitate daily for two months. Enrollment for Cohort 1 ended on May 24, 2019. Participants in the second cohort will be instructed to take 48,000 IU of vitamin A palmitate daily for one month. Participants in both cohorts will continue in the study for one month after ending Vitamin A supplementation. Participants in Cohort 1 may enroll into Cohort 2 as long as their last intake of vitamin A palmitate was greater than two months prior to their enrollment into Cohort 2.

Outcome Measures: For each cohort, the primary outcome is the measurement of dark adaptation parameters (thresholds and kinetics) by the following: dark adaptation times as measured by the AdaptDx comparing before and after vitamin A palmitate supplementation and dark adaptation parameters as measured by the Medmont comparing before and after vitamin A palmitate supplementation. The primary outcome will be assessed at Month 2 in the first cohort and Month 1 in the second cohort. For both cohorts, the secondary outcomes include changes in low luminance visual acuity (LLVA) and changes in patient reported outcomes as measured by the low luminance questionnaire (LLQ). The secondary outcomes also include measurement of dark adaptation parameters (thresholds and kinetics) comparing baseline and one month after completing supplementation (Month 3 in Cohort 1 and Month 2 in Cohort 2).

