3.0 PARTICIPANTS

Five participants with AMD who met the eligibility criteria were enrolled into the first cohort. Enrollment for Cohort 1 was halted on May 24, 2019 to focus on enrollment for Cohort 2. For the second cohort, up to five participants with AMD who meet the eligibility criteria may be enrolled in this protocol. Up to five additional participants may be accrued in the second cohort to account for participants who withdraw from the study prior to receiving one month of study supplementation for a reason unrelated to an adverse reaction. Participants in Cohort 1 may enroll

into Cohort 2 as long as their last intake of vitamin A palmitate was greater than two months prior to their enrollment into Cohort 2.

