4.0 STUDY DESIGN AND METHODS

This is a prospective, uncontrolled, single center, pilot study to investigate the potential efficacy and safety of taking 16,000 IU (Cohort 1) or 48,000 IU (Cohort 2) of vitamin A palmitate in improving dark adaptation in participants with AMD and abnormal dark adaptation.

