8.2 Secondary Outcomes

The secondary outcomes include changes in LLVA and patient reported outcomes as measured by the LLQ comparing baseline to the following timepoints:

- Completion of supplementation (Month 2 in Cohort 1 and Month 1 in Cohort 2)
- One month after completing supplementation (Month 3 in Cohort 1 and Month 2 in Cohort 2)

The secondary outcomes also include the measurement of dark adaptation parameters (thresholds and kinetics) by the following:

- Dark adaptation times as measured by the AdaptDx comparing baseline and one month after completing supplementation (Month 3 in Cohort 1 and Month 2 in Cohort 2).
- Dark adaptation parameters as measured by the Medmont comparing baseline and one month after completing supplementation (Month 3 in Cohort 1 and Month 2 in Cohort 2).

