4.0 DEFINITIONS

Treatment completion visit: The visit corresponding to completion of treatment, occurring at Month 2 in Cohort 1 and Month 1 in Cohort 2. The primary outcome is assessed at this visit.

Post-treatment follow-up visit: The final study visit which occurs one month after completion of treatment, corresponding to Month 3 in Cohort 1 and Month 2 in Cohort 2.

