Cells highlighted in green correspond to the primary outcome analysis; cells highlighted in yellow correspond to secondary analyses and the remaining analyses correspond to exploratory analyses.

^a Paired t-test comparing RIT at treatment completion visit or post-treatment follow-up visit vs. baseline at two-sided type 1 error rate of 5%.

^b Mixed-effects longitudinal model conducted at two-sided type 1 error rate of 5%. The coefficient β_1 corresponds to the estimate of the mean rate of change(monthly) in DA RIT. [COV] covariance structure provided the best model fit.

^c Treatment completion visit corresponds to Month 2 in Cohort 1, and Month 1 in Cohort 2. Post-treatment follow-up visit corresponds to Month 3 in Cohort 1, and Month 2 in Cohort 2.

^d Δ implies change from baseline.

Programming note: Replace [COV] with actual covariance structure that provided the best model fit.

Table 10. Analysis of Secondary Outcome of Change in LLVA Total Letters Read from Baseline in the Study Eye and Corresponding Exploratory Analyses

Visit ^c	Cohort 1						Cohort 2					
	Total Letters Read			Paired T-Test ^a			Mixed-Effects Model ^b			Total Letters Read		
	Mean	(95% CI)	p-value	β_1	SE (β_1)	p-value	Value	Value	Δ^d	Mean	(95% CI)	p-value
Baseline												
N	x									x		
Mean (SD)	x.x (x.xx)									x.x (x.xx)		
Median	x.x									x.x		
Range (min, max)	(x, x)									(x, x)		
Treatment Completion												
N	x									x		
Mean (SD)	x.x (x.xx)			x.x (x.xx)						x.x (x.xx)		
Median	x.x			x.x						x.x		
Range (min, max)	(x, x)			(x, x)						(x, x)		
Statistical Test												
	x.xx			x.xxx			x.xxx		x.xxx	x.xxx		
											x.xxx	
												x.xxx
Post-treatment Follow-up												
N	x									x		
Mean (SD)	x.x (x.xx)			x.x (x.xx)						x.x (x.xx)		
Median	x.x			x.x						x.x		
Range (min, max)	(x, x)			(x, x)						(x, x)		
Statistical Test												
	x.x			x.xxx			x.xxx		x.xxx	x.xxx		
											x.xxx	
												x.xxx

Cells highlighted in yellow correspond to the secondary outcome analysis, and the remaining analyses correspond to exploratory analyses

^aPaired t-test comparing LLVA at treatment completion visit or post-treatment follow-up visit vs. baseline at two-sided type 1 error rate of 5%.

^bMixed-effects longitudinal model conducted at two-sided type 1 error rate of 5%. The coefficient β_1 corresponds to the estimate of the mean rate of change (monthly) in LLVA total letters read. [COV] covariance structure provided the best model fit.

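### No estimate is planned of the change from the on-supplement to the off-supplement visit, and Model 1's single straight line cannot show a reversal

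*SAP*

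**What the plan says.** Protocol 4.0 describes the design: "This is a prospective, uncontrolled, single center, pilot study to investigate the potential efficacy and safety". There is no concurrent control. The Précis adds an off-supplement period: "Participants in both cohorts will continue in the study for one month after ending Vitamin A supplementation".

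SAP 4.0 defines the two visits that matter here. Treatment completion is "The visit corresponding to completion of treatment, occurring at Month 2 in Cohort 1 and Month 1 in Cohort 2". Post-treatment follow-up is the last visit, a month later: Month 3 for the first cohort, Month 2 for the second.

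The primary RIT analysis (SAP 9.1) is a paired t-test of treatment completion against baseline. The secondary RIT analysis (SAP 10.3) "will be conducted comparing baseline to post-treatment follow-up visit in each cohort (Table 9, Listing 1"). The footnote to Table 9 confirms that both tests share one reference: "Paired t-test comparing RIT at treatment completion visit or post-treatment follow-up visit vs. baseline". Protocol 8.2 sets the same off-supplement contrast, "comparing baseline and one month after completing supplementation (Month 3 in Cohort 1 and Month 2 in Cohort 2").

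SAP 11.1 adds Model 1 for Cohort 1 only. It has a random intercept and one linear monthly slope, β1, with the difference from baseline given as 2β1 at Month 2 and 3β1 at Month 3.

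On washout, Protocol 3.0 lets people from the first cohort join the second, "as long as their last intake of vitamin A palmitate was greater than two months prior to their enrollment into Cohort 2".

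**The concern.** Without a control arm, a change in RIT between baseline and treatment completion can come from the supplement, from practice on a psychophysical test, or from drift. The visit one month after stopping bears on this. A supplement effect would tend to fade once intake stops, while a practice effect or steady drift would tend to persist or grow. The quantity that speaks to this is the within-participant change from treatment completion to follow-up, and the plan gives no estimate or interval for it for any outcome.

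The data are already being collected. At stake is whether the report can say, with a stated uncertainty, how much of any change was lost after stopping. This matters most in Cohort 2, which was opened because Cohort 1 showed no significant improvement and for which no longitudinal model is planned.

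**Working it through.** The plan has no figure to reproduce: SAP 5.1 says no sample size calculation was made, and the documents give no SD, effect size or correlation for RIT change.

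**1. Planned contrasts** (B = baseline, C = treatment completion, F = follow-up)

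| Outcome | C vs B | F vs B | F vs C |
|---|---|---|---|
| RIT | SAP 9.1 | SAP 10.3 | none |
| AdaptDx and Medmont parameters | SAP 9.2 | SAP 10.4 | none |
| LLVA | SAP 10.1, 11.2 | SAP 10.1, 11.2 | none |
| LLQ | SAP 10.2, 11.3 | SAP 10.2, 11.3 | none |

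Tables 9–11 have no F vs C row. Tables 15, 17 and 18 and Listings 1–3 give change from baseline only.

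**2. What Model 1 reports under reversal.** Because the model is linear in time, its Month 2 to Month 3 change is 3β1 − 2β1 = β1, in the same direction as the change on supplement. For balanced data with a random intercept, the fixed slope equals the least-squares slope, Σ(t − t̄)y / Σ(t − t̄)².

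With visits at 0, 2 and 3 months, t̄ = 5/3, the deviations are −5/3, 1/3 and 4/3, and the sum of squares is 42/9 = 14/3.

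- Full reversal, y = (0, −d, 0): β1 = −(1/3)d ÷ (14/3) = −d/14 = −0.07d. The model reports −0.14d at Month 2 and −0.21d at Month 3; the true values are −d and 0.
- Persistent shift, y = (0, −d, −d): β1 = −(5/3)d ÷ (14/3) = −5d/14 = −0.36d.

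SAP 11.1 does not say whether Month 1 enters the model. With visits 0, 1, 2 and 3 (deviations ±1.5 and ±0.5, sum of squares 5):

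- Full effect from Month 1, then full reversal: β1 = 0.
- Ramp to −d at Month 2, then full reversal: β1 = (0.25d − 0.5d)/5 = −0.05d.
- Persistent shift from Month 1: β1 = −1.5d/5 = −0.30d.

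In each case the slope responds more to a lasting shift than to a reversible one. A different covariance structure, which the Table 9 footnote allows, would change these values but not the straight-line constraint.

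**3. What can be recovered from Table 9.** If the same participants contribute at both visits, the mean reversal is the difference between the two mean changes. Its SE needs Var(F − C) = Var(F − B) + Var(C − B) − 2Cov(F − B, C − B), and the table does not print the covariance. If both changes have SD s and correlation ρ, the SD of F − C is s√(2(1 − ρ)): 1.18s at ρ = 0.3, 1.00s at 0.5 and 0.77s at 0.7. These correlations are assumed.

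**4. Precision of the added contrast.** With n = 5 (SAP 5.1) and 4 df, the 95% CI half-width is 2.776/√5 = 1.24 SD of the paired difference. Power of a two-sided 5% test is 0.40 for a true reversal of 1.0 SD and 0.71 for 1.5 SD; it reaches 80% at about 1.68 SD. For assumed SDs of the difference of 2, 4 and 6 minutes:

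- half-width: 2.5, 5.0 and 7.5 minutes;
- reversal detectable with 80% power: 3.4, 6.7 and 10.1 minutes.

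**The case against.** The strongest reply is that little is missing. Protocol 9.1 calls the analyses mainly descriptive and by participant. Listings 1–3 print each participant's three visits together, and SAP 14.0 allows plots over time. Follow-up versus baseline is itself a planned estimate of how far participants remain from their starting point. All analyses are exploratory (SAP 5.0), and another interval from five people will be wide. This stands as a limit on weight. With Listing 1 a reader can calculate each reversal by hand, and the interval too. But distance from baseline is a different quantity from what was lost since treatment completion, and the existing t-tests share the same imprecision.

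Three stronger readings are tempting, and the documents do not support them.

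- A reader might infer that reversal will be concluded when the completion test is significant and the follow-up test is not. No section states such a rule or a reversal hypothesis. If someone did read the results that way, simulations with n = 5, no reversal and an assumed correlation of 0.5 between the two changes give the pattern in 9.9%, 18.3%, 15.8%, 6.8% and 0.2% of trials for shifts of 0.5, 1, 1.5, 2 and 3 SD; a direct paired test rejects in about 5%. The power gain is not assured. Under full reversal of 1 SD the direct test has about 31%, 40% and 59% power at correlations of 0.3, 0.5 and 0.7, against about 38% for the two-test pattern.
- A reader might infer that reversal would settle the cause. It would not, in a small, uncontrolled study. Some practice may also precede baseline, because Appendix 2 calls for earlier AdaptDx testing and some participants come from other dark adaptation protocols (Protocol 4.1).
- A reader might want serum vitamin A to decide attribution. The hypothesis in Protocol 1.0 is a local deficiency in patients whose serum levels are not deficient, so a serum rule has no footing in the plan.

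**Conclusion.** The point holds as a gap in planned estimates, not in data collection. No outcome has a planned estimate or interval for the on-to-off change, and the only model that uses both later visits is constrained so that it cannot show a reversal: β1 is −0.07d under full reversal and −0.36d under a persistent shift, for visits at 0, 2 and 3 months with balanced data and a random intercept.

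The added contrast would help with interpretation but would not be decisive. Its interval is about ±1.24 SD of the difference at n = 5. Absence of reversal at one month would not count against an effect, because carry-over is possible. That possibility is inferred from the re-entry rule of more than two months off; the protocol gives no reason for that rule. This is an inexpensive improvement and does not invalidate the planned analyses.

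**What to change.** - In SAP 10.3 and 10.4, and in 11.2 and 11.3 for LLVA and the LLQ composite, add the within-participant difference, post-treatment follow-up minus treatment completion, by cohort, with mean, 95% CI and individual values, labelled exploratory.
- Show it as a row in Tables 9, 10 and 11 (composite score) and as a column in Listings 1–3. The curve parameters and Medmont thresholds are analysed at the NEI and are not in those tables (SAP 2.0), so require the same contrast in the NEI output.
- In Model 1, and in the matching LLVA and LLQ models, replace linear time with visit as a categorical factor, so that the same contrast can be estimated.
- State beside the result that the interval is wide at n = 5 and that absence of reversal at one month does not rule out an effect.
- Optionally, list serum vitamin A beside RIT as context only. Appendix 2 schedules it at screening and follow-up visits but not at baseline, so the baseline row would carry the screening value.

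The cost is SAP wording, a few table rows, one column per listing and one more unadjusted exploratory interval per outcome. No new visits or tests are needed.

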10.4 Dark Adaptation Parameters

A similar analysis to the primary outcome analysis for dark adaptation parameters described in Section 9.2 will be conducted comparing baseline to post-treatment follow-up visit in each cohort. All dark adaptation parameters will be analyzed by researchers at the NEI.

11.0 EXPLORATORY ANALYSES

11.1 Dark Adaptation Times

To explore the effect of within-subject correlation, a mixed effects model (Model 1) will be fit using PROC MIXED in SAS to assess mean change from baseline in RIT in the study eye at the treatment completion visit and post-treatment follow-up visit in Cohort 1.

$$\text{Model 1: } \hat{Y}_{ij} = \beta_0 + \beta_1 * \text{Time}_j + b_i + \varepsilon_t$$

Where:

\hat{Y}_{ij} = Estimate of mean RIT for participant i at timepoint j

β_0 = Estimate of mean RIT at baseline

β_1 = Estimate of mean rate of change (monthly) in RIT

Time_j = Time in months from baseline

b_i = Random effect for baseline RIT in the i^{th} participant

ε_t = Random variability not explained by the model, which is assumed to be normally distributed and independent across participants and time

Based on this model, the estimated mean difference in RIT between baseline and Month 2 is $2\beta_1$, and the estimated mean difference between baseline and Month 3 is $3\beta_1$. The following hypothesis will be tested at a type I error rate of 5%:

$$H_0: \beta_1 = 0$$

$$H_A: \beta_1 \neq 0$$

The results of this analysis will be summarized as in Table 9.

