9.0 STATISTICAL ANALYSIS

9.1 Primary Outcome Analysis

In this prospective, pilot study, analyses will be primarily descriptive and by participant. The study does not lend itself to a formal sample size calculation. This is a pilot investigation targeted as understanding changes in dark adaptation within a given participant before and after vitamin A palmitate supplementation. The number of participants with changes in dark adaptation parameters will be summarized. Changes in rod-intercept time on the AdaptDx will be calculated for each participant. Similarly, pre-bleach thresholds and kinetic parameters will be compared before initiating supplementation to after completing supplementation for Cohort 1 (Month 2) and Cohort 2 (Month 1).

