3.3 Study Population

Five participants with AMD who met the eligibility criteria were enrolled into Cohort 1. Enrollment for Cohort 1 was halted on May 24, 2019 to focus on enrollment for Cohort 2. Up to five participants with AMD who meet the eligibility criteria may be enrolled in Cohort 2. Up to five additional participants may be accrued in the Cohort 2 to account for participants who withdraw from the study prior to receiving one month of study supplementation for a reason unrelated to an adverse reaction. Participants in Cohort 1 may enroll into Cohort 2 as long as their last intake of vitamin A palmitate was greater than two months prior to their enrollment into Cohort 2.

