11.2 Low Luminance Visual Acuity (LLVA)

For each cohort, change from baseline in LLVA total letters read at the treatment completion visit and post-treatment follow-up visit will be assessed using Student's paired t-test similar to the analysis of primary outcome as outlined in Section 9.1 for the study eye. Additionally, a model similar to Model 1 will be fitted to assess the mean difference in total letters read in the study eye

at the treatment completion visit and post-treatment follow-up visit compared to baseline in Cohort 1 (Table 10).

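### Model 1 (SAP 11.1, reused in 11.2 and 11.3) has no between-participant variation in change, so its test of beta1 need not hold the stated 5% with five Cohort 1 participants

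*SAP*

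**What the plan says.** SAP 11.1 defines Model 1 for Cohort 1 as an intercept, a single slope on months from baseline, a participant term and an error. The participant term is a "Random effect for baseline RIT in the" i-th participant, that is, a level only. The error is "Random variability not explained by the model, which is assumed to be normally distributed and independent across participants and time". Of beta1 = 0 the section says "The following hypothesis will be tested at a type I error rate of 5" per cent, and footnote b of Table 9 repeats it: "Mixed-effects longitudinal model conducted at two-sided type 1 error rate of 5" per cent.

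Section 11.2 extends this to LLVA ("a model similar to Model 1 will be fitted to assess the mean difference in total letters read in the study eye"), and 11.3 does the same for the LLQ composite. For Tables 9-11 the programming note reads "Replace [COV] with actual covariance structure that provided the best model fit". No candidate structures, selection criterion or degrees-of-freedom method are listed.

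On numbers, SAP 3.3 states: "Five participants with AMD who met the eligibility criteria were enrolled into Cohort 1". Section 11.1 names treatment completion (Month 2) and post-treatment follow-up (Month 3) against baseline. It does not say whether the Month 1 measurement enters the model.

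**The concern.** With a random intercept only, visits from one participant are treated as independent information about the mean slope once that participant's level is removed. If participants truly change by different amounts, all of a participant's visits share that individual slope, and only five independent units inform the mean. The model nevertheless uses 9 residual df with three visits, or 14 with four, and its standard error for beta1 can be too small.

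Tables 9-11 print this p-value beside a paired t-test on the same people. A smaller Model 1 p-value could be read as extra evidence of change when it comes only from leaving out variation in response.

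**Working it through.** **Inputs.** From the SAP: n = 5; nominal two-sided 5%; visits at 0, 2, 3 months (or 0, 1, 2, 3 if Month 1 is used); participant intercept only; independent errors. Assumed: tau, the SD of true monthly slopes, and sigma, the SD of a single test, with tau/sigma varied because the documents give neither. A ratio of 0.5 means that true Month 2 changes have an SD of 2 × 0.5 = 1 single-test SD; a ratio of 1.5 means 3. Default containment df are assumed for PROC MIXED.

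**Set-up.** In complete, balanced data with a positive estimated intercept variance, the Model 1 slope is the mean of the participants' least-squares slopes. With T visits and Sxx = Σ(t − mean t)²:

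- Model 1 variance of beta1 = MSE/(n·Sxx), on df = n(T−1) − 1. Three visits: Sxx = 4.67, df = 9. Four visits: Sxx = 5, df = 14.
- True variance = sigma²(1+k)/(n·Sxx), with k = Sxx·tau²/sigma².
- Expected MSE = sigma²[n(T−2) + (n−1)(1+k)]/df.

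**Plan's own figure.** With tau = 0, k = 0, the expected MSE is sigma², and the test statistic is exactly F(1, df). The stated 5% is reproduced.

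**Example, tau/sigma = 1.** Three visits: 1+k = 5.67 and expected MSE = (5 + 4×5.67)/9 = 3.07 sigma², so the model states 3.07/5.67 = 54% of the true variance. Four visits: 1+k = 6 and expected MSE = (10 + 4×6)/14 = 2.43 sigma², which is 40% of the true variance.

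**Limit for very large tau.** The test becomes a 4-df t statistic compared with the Model 1 critical value times √(4/df). Three visits: 2.262 × √(4/9) = 1.508, giving 20.6%. Four visits: 2.145 × √(4/14) = 1.146, giving 31.6%.

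**False-positive rates** (200,000 simulated trials per cell, n = 5, mean change zero, intercept SD 3 sigma):

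| Individual response | Visits | tau/sigma 0 | 0.25 | 0.5 | 1 | 1.5 | 2 |
|---|---|---|---|---|---|---|---|
| Linear to Month 3 | 0, 2, 3 | 5.0% | 6.4% | 9.4% | 14.6% | 17.2% | 18.5% |
| Linear to Month 3 | 0, 1, 2, 3 | 4.9% | 7.1% | 12.0% | 21.0% | 25.5% | 27.7% |
| Held after Month 2 | 0, 2, 3 | 5.0% | 5.6% | 7.2% | 10.6% | 13.0% | 14.5% |
| Held after Month 2 | 0, 1, 2, 3 | 4.9% | 5.9% | 8.6% | 14.9% | 19.6% | 22.4% |
| Fully lost by Month 3 | 0, 2, 3 | 5.0% | 4.3% | 2.8% | 0.9% | 0.3% | 0.1% |
| Fully lost by Month 3 | 0, 1, 2, 3 | 4.9% | 4.4% | 3.2% | 1.3% | 0.5% | 0.2% |

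Responses half lost by Month 3 lie between: 4.9% down to 2.9% with three visits, and 5.0% up to 6.0% with four, over tau/sigma 0.25 to 2.

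**Comparators.** In every cell, a one-sample t-test on the five participant slopes (4 df) and the paired t-test of baseline against Month 2 stay at 4.9-5.1%.

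**If the covariance structure is chosen by fit.** A rough check (300 runs, four visits, linear response, AIC choosing between random intercept and random intercept plus slope) gave about 8%, 11% and 7% at tau/sigma 0.5, 1 and 2.

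**The case against.** The strongest reply is that the direction of the error is not fixed. Cohort 1 stops supplementation at Month 2, so a response may fade by Month 3, and the test is then conservative. A reader might infer that the rate is inflated, to as much as 25%, whenever participants differ in response. The documents do not support that. Inflation requires the differences to persist sufficiently to Month 3. The 25% also needs Month 1 in the model and a large assumed ratio; with the three visits that 11.1 names, the rate cannot exceed about 21%. This objection stands and sets the bounds of the point. It does not rescue the stated 5%, and 11.1 itself assumes a straight line to Month 3.

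A reader might also take Protocol 9.1 ("The number of participants with changes in dark adaptation parameters will be summarized") as a premise that true responses differ. It plans descriptive counts, and observed changes differ through test-retest error alone. Variation in true response is therefore an assumption here.

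The Tables 9-11 notes allow a best-fitting covariance structure, so 11.1 is not the only written plan. That is a conflict between the two places, to be reconciled. With no candidates or criterion given, it cannot be counted as protection.

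Finally, all analyses are exploratory and the tables already carry valid paired t-tests. A reader might fear that a spurious Model 1 result could drive the higher dose. It cannot: both documents show that the second cohort was added on preliminary Cohort 1 data. This limits the importance. It does not excuse printing a 5% error rate that the test may not have.

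**Conclusion.** Model 1 as written in SAP 11.1 does not hold its stated 5% in general when true changes differ between the five Cohort 1 participants. At an assumed tau/sigma of 0.5 to 1.5:

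- linear change to Month 3: about 9-17% with visits 0, 2, 3, or about 12-25% with Month 1 added;
- response held after Month 2: about 7-13% with three visits;
- response fully lost by Month 3: below 5%.

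With no variation in response it is 5%. These figures rest on the assumed ratio, complete balanced data, default df and the 11.1 covariance kept unchanged. The point is minor: it concerns exploratory Cohort 1 analyses of RIT, LLVA and the LLQ composite, and leaves the primary paired t-test untouched.

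**What to change.** In SAP 11.1-11.3, compute each participant's slope and test the mean slope with a one-sample t-test on n − 1 = 4 df. Alternatively, report the beta1 estimate descriptively without a p-value. State in 11.1 whether Month 1 is used, and give the visits and df in footnote b of Tables 9-11. Reconcile the best-fit covariance wording there with the independent-error statement in 11.1.

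Do not treat a random-slope mixed model as an exact substitute. With five participants the slope variance can be estimated as zero, and the fit then falls back to Model 1.

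The cost is SAP wording and a few lines of code. The downside is wider intervals for beta1: the t multiplier rises from 2.26 (9 df) or 2.14 (14 df) to 2.78 (4 df).

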3.0 GENERAL REVIEW OF STUDY DESIGN

3.1 Study Design

The DA VitA AMD study is a prospective, uncontrolled, single center, pilot study to investigate the potential efficacy and safety of vitamin A palmitate dosing in improving dark adaptation in participants with AMD (without RPD) and abnormal dark adaptation.

The study will require five visits (screening, baseline, Month 1, Month 2, and Month 3) for Cohort 1 and four visits (screening, baseline, Month 1, and Month 2) for Cohort 2. Participants in Cohort 1 will be instructed to take vitamin A palmitate 16,000 IU daily by mouth for two months from baseline through Month 2 and will continue in the study through Month 3. Participants in Cohort 2 will be instructed to take 48,000 IU of vitamin A palmitate daily by mouth from baseline through Month 1 and will continue in the study through Month 2. The screening visit must occur between 60 days and one day prior to the baseline visit while Months 1, 2 and 3 visits must be conducted within a window of \pm 14 days from the target day. The tests scheduled at each visit may be split and completed within seven days (including the 7th day) from the visit date. At each visit, the participant will undergo a review of systems, such as an assessment of headache frequency and

severity, as well as an assessment of safety variables. A complete ophthalmologic examination will be performed at each visit to measure outcome variables. If participants in either cohort cannot tolerate the prescribed dose of vitamin A palmitate, they will be instructed to stop taking the supplement and they will be removed from the study.

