11.3 Low Luminance Questionnaire (LLQ)

For each cohort, change from baseline at the treatment completion visit and post-treatment follow-up visit for each subscale and the composite score will be assessed using Student's paired t-test similar to the analysis of the primary outcome as outlined in Section 9.1. Additionally, a model similar to Model 1 will be fitted to assess the mean difference in the composite score at the treatment completion visit and post-treatment follow-up visit compared to baseline in Cohort 1 (Table 11).

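### Exploratory Model 1 (Cohort 1) fixes the off-supplement Month 3 change at 1.5 times the Month 2 change, so it cannot assess the two visits separately

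*SAP*

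**What the plan says.** SAP 11.1 fits Model 1 in Cohort 1 to explore within-subject correlation and "to assess mean change from baseline in RIT in the study eye at the treatment completion visit and post-treatment follow-up visit". The model has an intercept, one slope β1 on months since baseline, a participant random effect and an error term "assumed to be normally distributed and independent across participants and time". It gives the Month 2 change as 2β1, then says that "the estimated mean difference between baseline and Month 3 is" 3β1. The single hypothesis tested is β1 = 0, two-sided at 5%.

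SAP 3.1 has Cohort 1 take supplement "by mouth for two months from baseline through Month 2 and will continue in the study through Month 3". SAP 4.0 defines the post-treatment visit as "The final study visit which occurs one month after completion of treatment, corresponding to Month 3 in Cohort 1".

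The form is reused in SAP 11.2 ("a model similar to Model 1 will be fitted to assess the mean difference in total letters read in the study eye") and SAP 11.3 ("a model similar to Model 1 will be fitted to assess the mean difference in the composite score"). In the SAP 18.0 shells, Tables 9–11 print β1, its standard error and a p-value. The Table 9 footnote says that β1 "corresponds to the estimate of the mean rate of change(monthly) in DA RIT". Footnotes and programming notes to all three tables leave the covariance structure to be filled in with whichever fitted best.

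**The concern.** Month 2 and Month 3 ask different questions: what happened on supplement, and what remained a month after stopping. A straight line through both presumes that any change continues at the same monthly rate once supplement stops. If the effect levels off or fades, the Month 3 data pull the slope down and the Month 2 estimate falls with it. The printed β1 would then be a monthly rate averaged over two months on supplement and one month off, and a real but fading effect could read as no change.

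The open covariance choice adds to this. When the true profile is not a line, β1 itself depends on the structure chosen, so selecting it after seeing about five participants' data also selects the estimate.

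**Working it through.** **The plan's own figures.** From E[Y] = β0 + β1·Time, the Month 2 change is 2β1 and the Month 3 change is 3β1, as SAP 11.1 states. The ratio is 3β1 / 2β1 = 1.5 for any non-zero β1.

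**What the slope returns.** Let M1, D and M3 be the true mean changes at Months 1, 2 and 3. With complete data and a random intercept, β1 is the within-participant least-squares slope. The SAP does not say whether Month 1 enters, so both visit sets are shown.

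- Visits 0, 2, 3: mean time 5/3, Sxx = 25/9 + 1/9 + 16/9 = 4.667, and β1 = (D/3 + 4·M3/3) / 4.667. Setting 2β1 = D gives M3 = 1.5D as the only solution.
- Visits 0–3: Sxx = 5 and β1 = (−0.5·M1 + 0.5·D + 1.5·M3) / 5.

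The documents give no fade rate, so three are assumed. For visits 0–3 the range runs from M1 = D (low end) to M1 = 0 (high end).

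| Assumed M3 | 2β1, visits 0, 2, 3 (truth D) | 3β1, visits 0, 2, 3 | 2β1, visits 0–3 (truth D) |
|---|---|---|---|
| D (no fade) | 0.71D | 1.07D | 0.60–0.80D |
| 0.5D (half fade) | 0.43D | 0.64D | 0.30–0.50D |
| 0 (full fade) | 0.14D | 0.21D | 0–0.20D |

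The full-fade row for visits 0, 2, 3 is β1 = (D/3)/4.667 = 0.0714D, so 2β1 = 0.143D and 3β1 = 0.214D.

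**Check by simulation.** Five participants, visits 0–3, assumed true changes of −2.5, −5 and 0 minutes, between-participant SD 5, residual SD 2, 200 runs. Model 1 averaged −0.47 minutes at Month 2 and −0.71 at Month 3. The same model with visit as a factor averaged −4.99 and 0.01.

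**Power.** Assume n = 5, visits 0, 2, 3, independent errors as 11.1 states, and D = 2 residual SDs.

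- Paired t-test, Month 2 versus baseline: noncentrality 2·√5/√2 = 3.16 on 4 df, power 66%.
- Categorical Month 2 contrast: the same noncentrality on 8 df, power 79%.
- Slope test on 9 df (200,000 simulations): 83% with no fade, 26% with half fade, 1% with full fade. The last is below 5% because the misfit of the line inflates the residual variance.

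The slope test drops below the categorical contrast once about 4.5% of D is lost by Month 3, and below the paired test at about 17%. These break-even points move with the assumed D. With Month 1 included and no fade, slope power is 67%, 88% or 93% for M1 = D, 0.5D or 0, against 83% for the categorical contrast. With no change at any visit, the slope test's simulated type I error is 4.9%.

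**Covariance choice.** The SAP names no candidates, so AR(1) and spatial power with ρ from 0.5 to 0.8 are illustrations (visits 0, 2, 3).

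| 2β1 | Random intercept | AR(1) | Spatial power |
|---|---|---|---|
| No fade | 0.71D | 0.75–0.78D | 0.67–0.68D |
| Half fade | 0.43D | 0.50–0.56D | 0.34–0.36D |
| Full fade | 0.14D | 0.25–0.33D | 0.01–0.04D |

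With visit as a factor and complete data, the point estimates do not depend on the structure, but their standard errors do. At ρ = 0.5 and unit variance, the per-participant variance of the Month 2 difference is 1.0 under compound symmetry and 1.5 under spatial power.

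**The case against.** The strongest reply is that nothing important rests on Model 1. Paired t-tests at both visits cover rod intercept time (SAP 9.1, 10.3), LLVA (11.2) and LLQ (11.3). Tables 9–11 print these beside β1, Listings 1–3 give each participant's values, and Table 15 adds Month 1. All analyses are exploratory (SAP 5.0, 5.6), and Cohort 1 is closed with preliminary results known (SAP 1.1, 3.3). All of that stands and sets the severity.

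Second, the tables print β1, labelled as a monthly rate, and not 2β1 or 3β1. This is true of the shells, but SAP 11.1 says the model assesses change at both visits and supplies the conversion.

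Third, the harm depends on an assumed fade. The gap of more than two months before re-entry to Cohort 2 (SAP 3.3) does not presume loss within one month, and with no fade the slope test has slightly more power on visits 0, 2, 3. That also stands. Even then, though, 2β1 understates the Month 2 change by 29%.

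Fourth, the covariance wording is a separate inconsistency. The 1.5 ratio does lie in the fixed effects, and no covariance choice removes it. The two are linked because misfit of the line is what makes β1 depend on the structure. Exploring within-subject correlation does not require a linear mean either, since a random intercept works equally well with a visit factor.

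**Conclusion.** The concern holds, at minor severity. As written, Model 1 cannot do what SAP 11.1 says it does: one slope cannot assess an on-supplement and an off-supplement change separately. The 1.5 ratio is exact and needs no assumption. The size of the distortion rests on the assumed fade and on whether Month 1 enters: 2β1 recovers 0.60–0.80D with no fade and 0–0.20D with full fade. The power figures also rest on D = 2 residual SDs and n = 5.

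The consequence is a potentially misleading β1, standard error and p-value printed beside sound results in three tables. If nothing changes at any visit, β1 is 0 and the test is valid. No primary or secondary result is affected.

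**What to change.** - In SAP 11.1, and in the models of 11.2 and 11.3, replace linear time with visit as a categorical factor, keep the participant random intercept, and state whether Month 1 is included.
- Fix that covariance. Remove the wording and programming notes under Tables 9–11 that leave it to be chosen by fit.
- Delete the 2β1 and 3β1 statements. Replace the β1 columns with Month 2 minus baseline, Month 3 minus baseline, and Month 3 minus Month 2.
- Label the change as made after the preliminary Cohort 1 results were known (SAP 1.1).

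The cost is SAP wording and three table shells. With five participants, residual degrees of freedom fall from 9 to 8 (visits 0, 2, 3) or from 14 to 12 (visits 0–3). If the effect does not fade, power on visits 0, 2, 3 is slightly lower (79% against 83% at D = 2 SDs). With complete data the first two contrasts repeat the paired mean changes, so the only new estimate is Month 3 minus Month 2.
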